Secondly, the mHealth tool has been used previously for health promotion where it improved knowledge in sexual reproductive health and facilitated behavior change (Ippoliti & L'Engle, 2017). The IMB model posits that provision of information and motivation influences behaviours. We hypothesize that the CFLU tool will address existing knowledge gaps among YLWH through provision of health messages about HIV, ART and medication adherence. Daily pill reminders and visit reminders will motivate youth and will help to address forgetfulness and busy schedules, factors which were the main causes of medication non-adherence and missed visits in the Call for Life study. Addressing these factors will influence adherence behaviours.

Prior work suggests that patients with higher HIV knowledge are twice as likely to keep their appointments as those who are less knowledgeable. Knowledge of HIV coupled with a good client-provider was associated with increased CD4 count and a five-fold likelihood of achieving undetectable VL (Jones, Cook, Rodriguez, & Waldrop-Valverde, 2013). Lack of knowledge of correct dosing and time to take drugs was associated with non-adherence in those starting ART (Miller et al., 2003). HIV knowledge has also been shown to be associated with improved quality of life (Swindells et al., 1999).

Lastly, evaluation of the effect mHealth tool will include assessment of stigma scores at baseline and follow-up, HIV knowledge at baseline and follow-up, and adherence as measured by clinic attendance (visit adherence), phone interaction and viral suppression.

The IMB model was chosen because the intervention will provide information through health tip messages and motivation through daily calls. According to prior recipients of the CFLU mHealth intervention, voice calls and voice tones encouraged and motivated them to continue taking medication, which impacted their behaviours including honoring clinic visit appointments, taking medication on time and willingness to report any symptoms they may have had. These factors may have improved clinic attendance, ART adherence and viral suppression. This model is a better fit for the CFLU mHealth tool than similar behavior models e.g. the Capability-Opportunity-Motivation-Behavioral (COM-B) model.

[figure not shown]
CHAPTER TWO: LITERATURE REVIEW

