Ratio of sample size. Unexposed/Exposed:	1
Percent of Unexposed with Outcome:	79
Percent of Exposed with Outcome:	94
Odds Ratio:	4.2
Risk/Prevalence Ratio:	1.2
Risk/Prevalence difference:	15

	Kelsey	Fleiss	Fleiss with CC
Sample Size - Exposed	81	80	93
Sample Size-Noneexposed	81	80	93
Total sample size:	162	160	186

References

Kelsey et al., Methods in Observational Epidemiology 2nd Edition, Table 12-15
 Fleiss, Statistical Methods for Rates and Proportions, formulas 3.18 & 3.19
 CC = continuity correction
 Results are rounded up to the nearest integer.
 Print from the browser menu or select, copy, and paste to other programs.

Results from OpenEpi, Version 3, open source calculator--SSCohort
 Print from the browser with ctrl-P
 or select text to copy and paste to other programs.

MAKERERE UNIVERSITY
 SCHOOL OF MEDICINE
 RENEWAL
 VALID UNTIL

★ 10 FEB 2023 ★

RESEARCH & ETHICS COMMITTEE
 103 FOR EACH ARM, KAMPALA

Factoring 10% loss to follow-up, the total sample size will be 206(103 for each arm, KAMPALA)

[figure not shown]
Data collection procedures:

The intervention is mobile phone based IVR. However, the CLFU trial found that, it was observed that a good number of participants (50 of 256) at the urban site were not enrolled due to absence of a basic mobile phone, or had malfunctioning phone keyboards (for Poster Exhibition at the 20th International Conference on AIDS and STIs in Africa (ICASA 2019). Therefore, we shall provide a basic mobile phone to everyone in the study (SoC and intervention arm). To avoid stigma associated with a particular phone, we shall get 4 or more types of basic phones. Issues regarding simcard registration will be dealt with by the individuals.

Four study questionnaires will be administered at baseline and 6-monthly until the 12-month exit visit.

The questionnaires will capture:

- Sociodemographic and medical history
- Stigma scores
- Knowledge assessment
- Sexual behavior assessment
- Knowledge of COVID-19 (only at baseline)

The data will be entered using REDCap. Blood for viral load will be collected at baseline and at the 6 and 12-month visit.

Intervention: mHealth CFLU tool

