The tool capitalises on a basic mobile phone's core utilities of voice and short messaging services. The system design, development, testing and evaluation was done by Janssen and the Grameen Foundation (<http://motechsuite.org/index.php/implementations>). In 2015, Janssen Global Public Health Research and Development, in close collaboration with the Infectious Diseases Institute Kampala (IDI), developed Call for Life Uganda (CFLU) tailored to the needs of PLHIV in Uganda. The CFLU system follows the Health Insurance Portability and Accountability Act (HIPAA) Privacy and Security rules. While the Privacy rules deals with electronic Protected Health Information, the security rule covers administrative, physical and technical safeguards to ensure confidentiality, integrity and security of electronic protected health information. Data transaction between patient and system is encrypted when it comes to human subjects. The system is password protected, and interaction of system and patient is personalised with a secret code. The system interacts with the patient through a basic mobile phone via a keypad and with the health worker through a web-based interface. The system has options to either use interactive voice response or short message service and the user has to make a choice, get a secret pin code which ensures privacy to enduser.

Screening-Enrolment procedures:

All potential participants will be written on the screening log, and a screening form completed, reasons for screen failure will be documented on the screening log. Following successful screening, the participant will be referred to the Research Assistant (RA) to receive a

thorough explanation of the study so and informed consent is obtained. The RA then administers the stigma questionnaire along with the sociodemographic and medical information, , HIV knowledge and sexual behaviour questionnaires. A client locator form will be completed which will help in physical contact tracing, and the participant will be registered on the enrolment log.

Randomisation will follow (see details of randomisation procedure below) thereafter and the result in the sealed envelope will dictate whether the patient will be registered onto the Call for Life System for the intervention or continue with standard of care as per MoH HIV Management guidelines.

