The Adult Care and Treatment Package includes the following services:(U. MoH, September 2014)

1. HIV counseling and testing
2. HIV prevention services
3. Nutritional Counseling and support
4. Opportunistic infection screening and management
5. Screening and management of non-communicable diseases
6. Diagnostics and laboratory monitoring
7. Sexual and reproductive health
8. Counseling and Psychosocial support
9. ARV preparation, initiation and monitoring
10. Adherence and retention into care
11. Palliative care
12. Mental health

[figure not shown]
[figure not shown]

Fig 5: Study Schema

The outcome variables include:

- ART adherence scores at 6 and 12 months, as assessed by HIV Care Card for those on SoC arm and Self- reported adherence to ART as depicted on the mHealth dash board.
- Viral load suppression at 6 and 12 months, as test results from blood collected at months 6 and 12 with time to viral suppression.
- Retention rates at 6 and 12 months with time to loss to follow-up
- Stigma scores at study start and end

Data Management Analysis Plan

Data collected on paper CRF will be entered using Research Electronic Data Capture software (REDCap) which is a safe, secure, HIPAA-compliant, web-based application and facilitates offline and online data entry. Data will be exported to STATA 14.0, for analysis. Data will then be backed up and archived in both soft and hard copy to avoid losses. The data collected will be stored securely under lock and key to maintain patient confidentiality.

Data regarding call details in the system will be extracted from CFL tool database, exported into Stata for analysis.

[figure not shown]
Visit dates will be extracted from database and proportions lost to follow-up drawn and time to loss to follow-up estimated. Viral load results will be extracted and time to viral suppression with survival analysis curves drawn for both arms.

Data from the MoH HIV card regarding the ART regimen and start dates will be transcribed to the data collection tool and later entered on the REDCap system.

General data analysis

Data will be analyzed at three levels, first at the univariate level, then at the bivariate level and lastly at the multivariate level. A consort diagram will be drawn to show the screening, enrolment, randomization, follow-up and analysis flow of the study.

Univariate Analysis

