Descriptive analysis will be done for the factors that influence adherence, virological suppression, stigma and retention in care. In addition, the distribution of the independent variables will be done with categorical data summarized using frequencies and percentages. Numerical data will be summarized using means and standard deviations for normally distributed data, and median and inter-quartile range for data that is not normally distributed.

Bivariate Analysis

The relationship between independent variables (age, gender, ART duration, marital status, education status, occupation and religion) and adherence and virological suppression will be analyzed using bivariate analysis made using cross tabular analysis and associations investigated using the Pearson Chi-square test.

The Chi-square test is based on the computational formulae below:

$$\chi^2 = \sum_{i=1}^r \sum_{j=1}^c \frac{(O_{ij} - E_{ij})^2}{E_{ij}}$$

Where

r is the number of categories of the ith explanatory variable

c is the number of categories of the dependent variable

[figure not shown]
O_{ij} is the observed number of observations in the ith explanatory

and jth dependent variable

E_{ij} is the expected number of observations in the ith explanatory?

and jth dependent variable

Further, odds ratios shall be used to analyze the relationship between the dependent variable and the independent variables. Variables found to be significant at p value of p ≤ 0.05 will be considered for the multivariable analysis.

Multivariate Analysis

Multivariable logistic regression will be used to determine the factors that influence adherence or virological suppression and retention in care. Variables found to be statistically significant at $p \leq 0.05$ in bivariate analysis and those considered to have a scientific explanation will be entered into the multivariable model.

The multivariate logistic regression adopted is based on the formulae below:

$$\ln \left[\frac{p_i}{1 - p_i} \right] = \beta_0 + \beta_1 X_1 + \dots + \beta_n X_n$$

[figure not shown]
Where;

X = independent variables

p_i = Probability of being adherent and virally suppressed

$1 - p_i$ = Probability of non-adherence or not suppressed virologically

β_0 = constant ; β_i = coefficient of the determinant

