 Not applicable

5. I have lost friends by telling them I have HIV

Yes
 No
 Not applicable
 Declined to answer

Section E: Subscale: Negative Self-Image

6. I feel that I am not as good a person as others because I have HIV

[figure not shown]
Yes
 No
 Declined to answer
 Not applicable

7. Having HIV makes me feel unclean

Yes
 No
 Declined to answer

8. Having HIV makes me feel that I'm a bad person

Yes
 No
 Declined to answer

Section G: Sub-scale: Public attitudes

[figure not shown]
9. Most people think that a person with HIV is disgusting

 Yes No Declined to answer

8. Most people with HIV are rejected when others find out

[figure not shown]
 Yes No Declined to answer

Study Staff		
Name	Signature	Date
Return appointment	Return Appointment	
study visit Date: _____ / _____ / _____	(Non-Study Visit: _____ / _____ / _____)	
Adapted from Stigma Scale Revised: Reliability and Validity of a Brief Measure of Stigma for HIV_ Youth. Ref: K. Wright et al. Journal of Adolescent Health		

CFL YOUTH STUDY

viii. DEMOGRAPHIC, SOCIO-ECONOMIC AND MEDICAL EVALUATION FORM

Section A: Patient Information													
3. Patient clinic # 

 	 	 	 	 	 	

							4. Study Number 

 	 	 	 	 	 	

						
3. Date Study Registration ____/____/____	4. Visit Code 

 	 	

 . 5. Enrolled in other studies?  Yes  No If Yes, Note here _____												
													

Section B: Demographics																					
1. Patient initials 

 	 	 	

				2. Residential Address 

 	 	 	 	 	 	 	 	

									3. Phone contact 

 	 	 	 	 	 	 	 	

								
4. Next of Kin a. _____ b. _____	5. Relationship with Patient a. _____ b. _____	6. Phone contact a. _____ b. _____																			

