18 FEB 2023										
RESEARCH & ETHICS COMMITTEE [name]										
i.	AIDS is a disease which has no cure									
ii.	Reduces the body's natural defense against illness									
iii.	Everyone with HIV has AIDS									
iv.	Bodies show signs of AIDS in a shorter time									
v.	Progression of HIV to AIDS can be slowed									

by getting into care and living positively

vi. Someone on ARVs who does not take ARV well will develop resistant virus

		
--------------------------	--------------------------	--------------------------

8. HIV Discordance is when a partner in a stable relationship tests HIV positive while the other tests HIV negative. Discordance is common. The following is true about discordance:

Agree (1) Disagree (2) Don't Know (3)

i. Discordance is a sure sign that someone has been unfaithful.

		
--------------------------	--------------------------	--------------------------

ii. A couple can remain discordant for a very long time

		
--------------------------	--------------------------	--------------------------

iii. The negative partner is always at risk.

		
--------------------------	--------------------------	--------------------------

iv. Couples can reduce risk by using condoms correctly and consistently during sex

		
--------------------------	--------------------------	--------------------------

v. HIV positive partner should start ARV's as soon as possible

		
--------------------------	--------------------------	--------------------------

9. The following is true about ART

Agree (1) Disagree (2) Don't Know (3)

i. When one is tested for HIV and started on ARVs that first treatment is called first line.

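### Stigma score is a listed outcome of the randomised comparison, but the plan only describes it: no scoring rule is stated and no baseline-adjusted comparison of the arms

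*Combined protocol and SAP*

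**What the plan says.** The outcome list for Study Objective 2 (section 3.4) has four entries: adherence scores, viral suppression, retention, and "Stigma scores at study start and end". Section 1.6 (Theoretical Framework) says that evaluating the tool's effect will include "assessment of stigma scores at baseline and follow-up, HIV knowledge at baseline and follow-up".

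The baseline measurement comes before allocation. In the screening and enrolment procedures, "The RA then administers the stigma questionnaire along with the sociodemographic and medical information", and randomisation follows, so both arms have a baseline score.

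The analysis text names stigma once, under Univariate Analysis: "Descriptive analysis will be done for the factors that influence adherence, virological suppression, stigma and retention in care". The bivariate chi-square step covers adherence and viral suppression. The logistic model covers adherence or suppression, and retention.

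On timing, the data collection procedures say "Four study questionnaires will be administered at baseline and 6-monthly until the 12-month exit visit", and stigma is in the list that follows. The outcome list and the header of the stigma form (Appendix vii) give study start and study end only.

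**The concern.** An outcome of a randomised trial needs an estimate of the difference between arms. For stigma the plan gives none. A report that followed the text could show stigma scores at two time points and still not say whether CFLU changed them. The baseline score, probably the best predictor of the end score, would go unused.

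The score itself is also undefined. The form has unequal response options and no total, subscale field or rule for unanswered items. If that choice is left open until data by arm are available, it can be made with the results in view.

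**Working it through.** **1. The plan's own figure.** The sample size rests on viral suppression (79% v 94%, two-sided 5%, 80% power, 1:1). Kelsey: (1.960 + 0.842)² × 0.865 × 0.135 × 2 / 0.15² = 81.5 per arm (stated 81). Fleiss gives 81 (stated 80), and 94 with continuity correction (stated 93). Allowing for 10% loss, 186 / 0.9 = 206.7 (stated 206). All agree to within one per arm. No calculation is given for stigma, so 93 evaluable per arm (186 in total) is taken as the working size.

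**2. Where each listed outcome is analysed (section 3.4).**

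| Outcome | Descriptive | Chi-square | Logistic | Survival curves |
|---|---|---|---|---|
| Adherence | yes | yes | yes | no |
| Viral suppression | yes | yes | yes | yes |
| Retention | yes | no | yes | time to loss to follow-up |
| Stigma | yes | no | no | no |

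Study arm is not among the independent variables listed for the bivariate step (age, gender, ART duration, marital status, education, occupation, religion).

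**3. The stigma form (Appendix vii).** Items 1–3 offer Yes, No and N/A. Items 4–6 offer Yes, No, N/A and Declined. Items 7–10 offer Yes, No and Declined. (The tenth item is misnumbered 8 on the form.) So N/A is possible on 6 of 10 items and Declined on 7 of 10. The three personalised-stigma items concern other people knowing the participant's status; one is "5. I have lost friends by telling them I have HIV". How N/A is handled therefore matters most there.

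**4. Why the rule must be stated.** Four Yes answers give a sum of 4. As a proportion of answered items they give 4/10 = 40% if all ten are answered, but 4/4 = 100% if the six items that allow N/A are all marked N/A. These are the extremes, but they show that the two natural scores can disagree.

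**5. What baseline adjustment gains.** Let r be the correlation between baseline and month 12 scores (assumed), with n = 93 per arm.

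- Unadjusted detectable difference: (1.960 + 0.842) × √(2/93) = 0.41 SD.
- Adjusted for baseline: multiply by √(1 − r²).
- Equivalent unadjusted total: 186 / (1 − r²).

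| r | Variance removed | Detectable difference (SD) | Equivalent unadjusted total |
|---|---|---|---|
| 0.3 | 9% | 0.39 | about 204 |
| 0.5 | 25% | 0.36 | 248 |
| 0.7 | 49% | 0.29 | about 365 |

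For a true difference of 0.4 SD, power is 78% unadjusted and 82%, 88% or 97% adjusted. A change-score analysis, multiplying by √(2(1 − r)) instead, gives 64%, 78% or 94%. It falls below the adjusted analysis at all three correlations.

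**6. HIV knowledge.** Section 1.6 names it beside stigma, but it is absent from the outcome list and from the analysis text.

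**The case against.** The strongest reply is that stigma is a minor outcome. It has no hypothesis in section 2.6, the planned paper on effect (List of possible manuscripts, III) covers adherence, retention and suppression, and the trial was not sized for it. That stands, and it is why the comparison should be labelled secondary. It does not explain why a listed outcome has no comparison between arms.

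A second reply is that the form is adapted from a published brief scale, whose source may contain a scoring key. That may be so. The fair statement is that the protocol gives no scoring rule, not that no usable score can be derived.

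Several stronger readings are tempting, and the documents do not support them:

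- **That the trial will produce a spurious stigma effect because N/A counts as No.** No such rule, and no simple-sum rule, appears anywhere. N/A is offered on all three personalised-stigma items. The risk is that the rule is open, not that a biased one has been chosen.
- **That the planned models cannot handle a score.** Logistic regression accepts a numeric covariate. The point is that stigma is not named as an outcome in either step.
- **That adjustment makes 206 participants worth about 275.** That is 206 / 0.75, which uses the enrolled number and one assumed correlation. With 186 evaluable it is 248 at r = 0.5, and only about 204 at r = 0.3.
- **That repeated statements on the knowledge form (Appendix ix, Section D) bias the comparison.** Six repeats are clear; for example "AIDS is a disease which has no cure" in item 7 restates item 1i. A seventh (7iv against 1v) differs in wording. Repetition reweights a total equally in both arms, so it does not bias the difference between them.

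**Conclusion.** The concern holds as a secondary-outcome point that should be corrected. Stigma is an outcome of the randomised objective, tied to the tool's effect and measured in both arms before randomisation, yet the plan only describes it. That the comparison and the scoring rule are absent can be read from the text and needs no assumption.

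The size of the gain does rest on assumptions: 93 evaluable per arm (the plan's 10% loss), a score analysed in SD units, and a correlation between 0.3 and 0.7 that the documents do not give. Across that range the detectable difference falls from 0.41 SD to between 0.39 and 0.29 SD. At the lower end the gain in precision is small, and the main benefit is having an estimate of effect at all. Adjustment uses one degree of freedom and no extra data, but it can be applied only once the score is defined.

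**What to change.** 1. **Analysis.** Add to the analysis plan, labelled secondary: linear regression of the month 12 stigma score on arm and baseline score, reporting the adjusted mean difference with its 95% CI.
2. **Score.** State one rule before data by arm are seen, for example the proportion of answered items marked Yes. Say explicitly how N/A (items 1–6) and Declined (items 4–10) are handled, including a participant who marks all three personalised-stigma items N/A and so has no value for that subscale.
3. **Personalised stigma.** Show these three items separately. Split them only by disclosure at baseline (Appendix viii, Section C, item 14). Disclosure at follow-up arises after randomisation, and splitting on it would no longer be a clean randomised comparison.
4. **Form.** If baseline forms have already been completed, keep the existing tick boxes and apply the scoring rule alone. Changing the options midway would make baseline and month 12 scores non-comparable.
5. **HIV knowledge.** Add it to the outcome list and analyse it the same way, with a stated scoring key.
6. **Schedule.** Reconcile the 6-monthly statement with the start-and-end statements on whether stigma is asked at month 6.

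The cost is a few sentences in the analysis plan and a scoring key.

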Loss to follow-up: Missing 2 visits consecutively, not able to ascertain vitals

mHealth: use of mobile technology e.g. mobile phones and other wireless technology for health-related activities

Retention in care: Continuous engagement in clinical care for 1 year

Virological suppression: Viral load less than 1000 copies/ml

Youth Living with HIV/AIDS: Persons living with human immunodeficiency virus/ acquired immunodeficiency syndrome aged 15 to 24yrs (United Nations General Assembly Resolution A/RES/50/81 ("World Programme of Action for Youth to the Year 2000 and Beyond"))

LIST OF ABBREVIATIONS

AIDS: Acquired Immuno Deficiency Syndrome

cART: Combined Antiretroviral Therapy

CD4 cell: Cluster Differentiated cells

cDOT: Community based Directly Observed Treatment

CFLU: Call for Life Uganda

CITI: Collaborative Institutional Training Initiative

COVID-19: CORONA VIRUS DISEASE 2019

GCP: Good Clinical Practice

HIT: Health Information Technology

[figure not shown]
HIV RNA: Human Immunodeficiency Virus Ribonucleic Acid

HSP: Human Subjects Protection

IAC: Intensive Adherence Counselling

IDI: Infectious Diseases Institute

IVR: Interactive Voice Response

MoH: Ministry of Health

PEPFAR: President's Emergency Plan for AIDS Relief

PHS: Physical Health Scores

PLWH: People living with HIV

SMS: Short Messaging Service

[figure not shown]
UBOS: Uganda Bureau of Statistics

UNAIDS: United Nations Programme on HIV and AIDS

UPHIA: Uganda Population-Based HIV Impact Assessment

VL: Viral load

YLWH: Youth living with HIV

ABSTRACT

Version 3.2, 12th Jan 2022

Background:

An estimated 3.9 million[2.1–5.7 million] youth were living with HIV (YLWH) globally in 2017, most of whom live in sub-Saharan Africa (Avert.Org, 2019; UNAIDS, 2018b). Young people are the only population group in which AIDS-related deaths are increasing (UNAIDS, 2019a). AIDS is the leading cause of death among young people in sub-Saharan Africa (Avert.Org, 2019).

In Uganda, there were 160,000 YLWH in 2018 (UNAIDS, 2019b). An estimated 53,000 new HIV infections occurred among youth in 2018, accounting for 26% of HIV incidence in the country (Avert.Org, 2019).

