During enrolment, it is important to obtain the names and contact information for several individuals closely related to the participant (e.g., next of kin, friends, etc.). Such individuals can be contacted in the event that a participant does not return for follow-up visits. Physical contact tracing will happen if the patient takes 2 weeks past the scheduled visit.

Missed visit:

When the appointment is not honoured and the 14-day window passes, this is a missed visit. If a participant misses a visit (Visit window inclusive) a missed visit form is completed documenting the reason for missing (if known) and the attempts made to contact the participant, through mobile

phone or physical tracing. Several attempts to contact the participants must be made to ensure good retention. The attempts may include: Checking the General clinic schedule to sync the appointment visit, Calling the participant; Calling a relative who was disclosed to, or Visiting the participant's home: To minimise missed visits, through the web-interface on CFLU system, any dropped calls monitored on the dashboard, will trigger active follow-up and tracing of the participants.

Loss to follow-up:

If a participant misses 2 consecutive visits and unable to ascertain the vital status, this patient will be declared lost to follow-up, alternatively, if 3 months consecutively elapse, without acknowledging the patient's status, the patient will be labelled lost to follow-up. If a participant's whereabouts are not known for 3 months and the contact tracing is uneventful after 3 documented attempts, this participant is deemed lost to follow-up and a withdraw form is completed. In case the participant re-surfaces to the clinic when the study is still active/ongoing, the withdraw form is cancelled out and patient re-joins the study and a study visit is conducted.

Study Objective 3:

To evaluate the cost of mHealth in comparison to Standard of Care

Study design: Cost evaluation analysis

Study Purpose: To assess cost of mHealth intervention in comparison to standard of care

[figure not shown]
Primary outcome measure: Costs spent on the intervention participants in comparison to standard of care participants

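### Retention is defined as continuous clinical care, but the only planned derivation is loss to follow-up, which no youth of known status can meet

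*Combined protocol and SAP*

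**What the plan says.** The definitions list gives two separate terms. One is "Retention in care: Continuous engagement in clinical care for 1 year". The other is "Loss to follow-up: Missing 2 visits consecutively, not able to ascertain vitals".

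Under Study Objective 2 in section 3.4, the outcome list includes "Retention rates at 6 and 12 months with time to loss to follow-up". No numerator, denominator or rule for being in care accompanies it. The Data Management Analysis Plan gives one derivation: "Visit dates will be extracted from database and proportions lost to follow-up drawn and time to loss to follow-up estimated". The Multivariate Analysis paragraph then names retention in care as a dependent variable for logistic regression, which needs a defined yes/no value for each participant.

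The Loss to follow-up paragraph has three rules:

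- "If a participant misses 2 consecutive visits and unable to ascertain the vital status, this patient will be declared lost to follow-up";
- "if 3 months consecutively elapse, without acknowledging the patient's status, the patient will be labelled lost to follow-up";
- whereabouts unknown for three months, with three documented tracing attempts that did not find the participant.

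The Study visits paragraph schedules two follow-up visits, at day 168 and day 336, each with a 14-day window. Interim visits for illness or a repeat blood draw receive their own codes. The Missed visit paragraph lists ways to reach an absentee, including "Checking the General clinic schedule to sync the appointment visit", telephone calls and home visits. It adds that dropped calls seen on the CFLU dashboard start active tracing.

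On the care card, the plan states "Data from the MoH HIV card regarding the ART regimen and start dates will be transcribed to the data collection tool". The outcome list also uses the card for adherence in the standard-of-care arm.

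**The concern.** The definition concerns engagement in care, whereas the derivation concerns whether staff know where a participant is. The two can give opposite answers for the same person. Tracing widens the gap: each successful home visit or call to a relative makes a status known, and so takes a real drop-out or a death off the loss count.

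The listed outcome could then describe tracing effort more than engagement in care. Tracing effort is not the same in the two arms, because only CFLU participants receive the calls whose failure prompts it. A difference in retention could therefore appear with identical care.

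Retention also has uses beyond the outcome list. The third hypothesis in section 2.6 depends on the proportion in care, and two planned manuscripts concern retention.

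**Working it through.** **Rules applied to individuals**

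| Youth | In continuous care? | Two missed visits, vital status unknown | Three months, status unknown | Whereabouts unknown, tracing failed |
|---|---|---|---|---|
| Confirmed dead | No | Not met | Not met | Not met |
| Traced alive, has left care | No | Not met | Not met | Not met |
| Out of care between visits, attends months 6 and 12 | No | Not met | Not met if status is taken as known from attendance | Not met unless tracing failed in between |
| Stopped study visits, still in clinic care | Yes | Not met if the clinic-schedule check finds them | Same | Same |

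The first two rows do not depend on which database supplies the visit dates.

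**Timing**

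- The month-6 window closes at day 168 + 14 = 182. By then at most one scheduled follow-up visit can have been missed.
- A second can be missed only when the month-12 window closes, at day 336 + 14 = 350. The two-missed-visits rule therefore cannot contribute to a month-6 rate.
- The three-month rules might, but the plan does not say when the three months start.
- The one-year definition of retention cannot be applied at month 6 as written.

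**Size (illustration)**

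The plan states no retention target, so there is no planned figure to reproduce. The number per arm follows from the sample-size section: 93 × 1.10 = 102.3, rounded up to 103.

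Inputs:

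- Out of care at 12 months: 1 − 0.79 = 0.21. The 79% is the site-overall retention in Table 1 (net cohort 266) and is not shown there to be specific to youth.
- f, the share of those out of care whose status is known: not in the documents. Range assumed: 0.10 to 0.50.
- Retention reported as 1 − loss: assumed, because the plan does not say so.

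Formula: apparent retention = 1 − 0.21 × (1 − f). Out of care per arm = 103 × 0.21 = 21.6.

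| f | Out of care but not counted lost, per arm | Apparent retention |
|---|---|---|
| 0 | 0 | 79.0% |
| 0.10 | 21.6 × 0.10 = 2.2 | 1 − 0.189 = 81.1% |
| 0.50 | 21.6 × 0.50 = 10.8 | 1 − 0.105 = 89.5% |

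**Difference between arms**

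With equal true retention, the false difference is 0.21 × (f in the intervention arm − f in the control arm). For 0.50 against 0.25 it is 0.21 × 0.25 = 5.25 percentage points. The widest contrast in the assumed range, 0.50 against 0.10, gives 0.21 × 0.40 = 8.4 points. The documents give no arm-specific values.

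**The case against.** The best defence is that loss and retention are defined separately, and that keeping the word lost for unknown status is a legitimate convention. Nowhere does the plan equate retention with one minus loss. This stands, and it makes the overstatement conditional. It does not supply the missing rule: the loss derivation is the only one given, and the regression still needs a retention variable.

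A second defence is that the trial already collects much of what is needed. The six-monthly medical form has ART start and end dates with reasons for change or stopping, so a youth who stops ART but attends both visits may leave a dated record. Care follow-up is also six-monthly, so study and clinic visits may often coincide. Section 1.6 treats clinic attendance as a measure of adherence. All of this is correct and makes the remedy cheap, but the plan never says that these data feed the retention outcome.

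Three stronger readings are tempting, and the documents do not support them:

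- A reader might infer that youth who leave only the study are misclassified as lost. Someone still attending clinic would normally have known status, and the clinic schedule is checked after a missed visit. The plan is silent on how they are classified, which is a gap and not a demonstrated error.
- A reader might infer that the database holds only three contacts per person. Interim visits are coded as well, and the text refers to visit dates without saying study visits.
- A reader might infer that only regimen and start dates come from the care card. The card also supplies standard-of-care adherence.

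**Conclusion.** The point holds, and the plan should be changed. As written, deaths and youth traced alive but out of care meet no loss rule. Two scheduled visits cannot show continuous engagement, and the two-missed-visits rule cannot operate by month 6. Because one tracing trigger exists only in the intervention arm, ascertainment of status, and hence apparent loss, can differ by arm. All of this follows from the text without any assumption about numbers.

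The size is illustrative only. Apparent retention of about 81-90% instead of 79% rests on the site-overall figure, on an assumed 10-50% of known status, and on reporting retention as the complement of loss. That an arm difference can arise is established; that one will arise, or how large it would be, is not.

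The weight is moderate. Retention is a listed outcome but is absent from the specific objectives in section 1.3.2, and the sample size rests on viral suppression.

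**What to change.** For every randomised participant, including those who stop study visits where consent allows, transcribe clinic attendance and refill dates, transfer-out and death from the HIV care card. Combine these with the ART stop dates already on the six-monthly form.

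Write one retention rule for month 6 and one for month 12, with a stated window and denominator, and apply them identically in both arms. Count deaths and youth traced but out of care as not retained. Count documented transfer into care elsewhere as in care. Report study withdrawal and unknown vital status as separate categories and not as part of retention. Collecting care-card dates for everyone also makes the result less dependent on which arm was traced harder.

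The cost is a few more fields from a card already in use, modest abstraction time and a wording change to the outcome and analysis sections. The retention figure may also turn out less favourable.
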